**9.2.4 Individual Symptom items and Quality of Life**

EORTC, and Individual Symptom Items (ISI, NCI-CTC) as described in section 7 will be collected at predefined time points. A composite score for the EORTC questionnaire will be calculated following the EORTC scoring manual at each time point. In addition, individual items from these instruments will be summarized at each time point and patients’ profiles over time will be described graphically to assess which of these items fluctuate over time, or whether they capture patients’ symptoms in this post-op period. A descriptive analysis of individual symptoms reported will be performed. Most commonly reported and most distressing symptoms will be documented.

**Memorial Sloan-Kettering Cancer Center  
IRB Protocol**

**IRB#: 08-155A(8)**

**Table 4. Study Timetable**

	Pre-op Consent Visit	Post-op Week 1	Post-op Week 2	Post-op Week 3	Post-op Week 4	Post-op Week 5	Post-op Week 6	Post-op Week 6-8
Informed Consent / Research Authorization	X							
Paper Baseline Questionnaire	X							
Online Patient Study (CTC)- Questionnaire	X	X	X	X	X	X	X	
Online Patient Study (EORTC)- Questionnaire	X			X			X	
Patient Satisfaction Questionnaire								X
Clinician Feedback Email Questionnaire								X

**Pre-op, Pre-operative; Post-op, Post-operative**

**10.0 CRITERIA FOR REMOVAL FROM STUDY**

If a patient is enrolled but does not subsequently undergo planned surgery, she will be removed from the study and will not be evaluated in the feasibility assessment. A participant can be removed from the study at any time if her doctor believes it is in her best interest to do so, or if she develops cognitive impairment as judged by her doctor or noted in the medical record. A participant may withdraw from the study at any time.

**11.0 BIOSTATISTICS**

**11.1 Sample Size and Accrual**

The sample size of 110 patients is based on the personnel resources (one dedicated clinical fellow) and time available (approximately one year) to conduct this study. A responder is defined as a patient who logs in and completes at least half of the questionnaire at least 4/7 potential logins. The hypotheses being tested are: 80% is considered acceptable whereas 65% is considered too low. The study requires 79 patients to show a difference from 65% to 80% in percent responders with 90% power and type I error of 4%. If at the end of the study 58/79 are responders then the study will conclude that the use of WEBCORE in this population is feasible.

[figure not shown]

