## Memorial Sloan-Kettering Cancer Center IRB Protocol

**IRB#: 08-155A(8)**

will notify the POA of the patient's gynecologic oncologist and the clinic nurse taking patient calls for that gynecologic oncologist that day. No specific responses to these emails will be required, but any actions taken in response to these alerts by clinicians will be tracked (ie, telephone calls, supportive medication prescriptions, new appointments made, etc) using a form emailed to the nurse after the automated email alert (Appendix 5) and the "Ambulatory Care Phone/Email Communication Form" in the EMR. The forms will be collected by the research fellow or by the designated RSA.

It will be emphasized to patients that there is no regular monitoring of information entered into WEBCORE, and that they should call their physician's office if they feel that they require medical attention. This will be emphasized to patients in the informed Consent, during a WEBCORE training session, and on the WEBCORE website. In addition, anytime a patient enters a potentially concerning response into WEBCORE, a popup box will appear on the screen reminding her to consider calling her physician.

If 80% of enrolled patients with home Internet access login to WEBCORE at least four times during the study period we will consider WEBCORE a strategy warranting larger scale evaluation. Patient assessment of the usefulness of WEBCORE will be measured via an exit survey. Clinician perceptions of the potential value of WEBCORE will be evaluated via an email survey and questions asked at a team meeting. Reasons for patient non-compliance will be assessed via results of the backup telephone calls to those who failed to login, and with the exit survey.

Potential benefits of this use of the WEBCORE platform in this context will be assessed by measuring the number and type of clinical interventions made in response to WEBCORE alerts, and by analyzing patient use of WEBCORE in relation to dates of surgery and development of documented post-surgical complications.

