## Memorial Sloan-Kettering Cancer Center IRB Protocol

**IRB#: 08-155A(8)**

We will consider the results of this feasibility study to suggest that WEBCORE is a strategy warranting larger scale evaluation if approximately 80% of enrolled patients login to WEBCORE at least four times from the time of enrollment until six weeks following surgery. Patient assessment of the usefulness of WEBCORE will be measured via an exit survey. Clinician perceptions of the potential value of WEBCORE will be evaluated via an email survey and questions asked at a team meeting. Reasons for patient non-compliance will be assessed via results of the backup telephone calls to those who failed to login, and with the exit survey.

Potential benefits of this use of the WEBCORE platform in this context will be assessed by measuring the number and type of clinical interventions made in response to WEBCORE alerts, and by analyzing patient use of WEBCORE in relation to dates of surgery and development of documented post-surgical complications.

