## **9.0 PRIMARY AND SECONDARY OUTCOMES**

### **9.1 Primary Outcome**

The primary objective of this study is to evaluate the feasibility of patients using WEBCORE to track their own symptoms and HRQL while recovering from laparotomy for presumed or confirmed gynecologic cancer. In this pilot feasibility study, we will measure several parameters related to patients' utilization of the WEBCORE system, in order to evaluate the potential for implementation of collecting patient self-reported measures in a gynecologic oncology practice and/or in clinical trials.

- To gauge patients' willingness to record their experiences we will record the ratio of the number of patients approached for study participation to the number who enroll. The proportion of patients approached versus consented will be tracked continuously by the Research Fellow and the designated Surgery RSA.
- We will evaluate the extent to which patients who enroll in the protocol use the WEBCORE system to self-report symptoms and HRQL. Specifically, we will measure how often each user accesses the WEBCORE system, and will note the time and date that utilization occurs. Perfect compliance would be logging on and completing all the questions seven times: once pre-operatively, and then weekly for six weeks following surgery. In keeping with standards for the assessment of feasibility of online platforms, as a crude measure of feasibility, we will consider the study results to suggest that WEBCORE is a strategy warranting larger scale evaluation if approximately 80% of participants login to WEBCORE at least four times during the study period [13]. In our analysis, we will look at WEBCORE utilization (1) over time and (2) in relation to the presence or absence of documented minor and major surgical complications. The proportion of users who logged in with or without a follow-up reminder email will be tabulated. We will assess for attrition of compliance over time by measuring the proportion of patients who login during each consecutive week of observation.
- Results of backup telephone calls made when patients have not logged in will be tabulated to assess if the reported symptoms of such patients differ from reports of patients who have logged in on time, and reasons for non-compliance.

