## Memorial Sloan-Kettering Cancer Center IRB Protocol

**IRB#: 08-155A(8)**

Based on prior MSKCC research in this population, we anticipate that 90% of approached patients will agree to participate, of which 75% will be regular email users [13]. We will track the proportion of patients approached who consent as one of the measures of feasibility. The proportion of patients approached versus consented will be tracked continuously by the Research Fellow and the designated Surgery RSA. There are approximately 570 laparotomies performed on the gynecology service annually (internal data). We anticipate that accrual for the study will be complete within 6-9 months. We will enroll the first 5 patients of 110 patients as a small pilot to identify potential problems and correct any issues that may arise. After the evaluation of the first 5 patients the accrual period will remain open until at least 80 evaluable patients are enrolled. The sequence of patient activities following accrual is shown in Figure 1.

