**IRB#: 08-155A(8)**

**11.2 Primary Objective**

The primary objective of this study is to evaluate the feasibility of patients using WEBCORE to track their own symptoms and HRQL while recovering from laparotomy for presumed or confirmed gynecologic cancer. We will calculate summary statistics for several measures of utilization, including the frequency with which each user logs in and completes a WEBCORE online questionnaire; the proportion of patients who log in at each sequential week of follow-up; and when utilization occurs in relation to surgery and/or complications. If at the end of the study 58/79 are responders (a responder is a person who has logged in at least 4/7 times and completed at least half of the questions each time) then we will conclude that the use of WEBCORE in this population is feasible. If this hypothesis is true, we will consider the study results to suggest that WEBCORE is a strategy warranting larger scale evaluation [13]. Baseline patient characteristics and disease information will be examined via a logistic regression for their relationship to a patient's likelihood of being a responder. The following predictors will be considered: type of cancer, type of surgery, stage of disease, computer experience/age/education

In our analysis, we will look at WEBCORE utilization (1) over time and (2) in relation to the presence or absence of documented minor and major surgical complications. We will tabulate the proportion of users who logged in with or without a follow-up reminder email. We will assess for attrition of compliance over time by measuring the proportion of patients who login during each consecutive week of observation. Results of backup telephone calls made when patients have not logged in will be tabulated to assess if the reported symptoms of such patients differ from reports of patients who have logged in on time, and reasons for non-compliance. We will calculate the proportion of WEBCORE responders compared to the total number of enrollees (responders: enrollees), as well as the proportion of responders compared to total number of patients eligible (responders: eligible). Baseline characteristics for those who refuse enrollment will be compared to those who agree to participate.

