**IRB#: 08-155A(8)**

**11.5 Missing Data**

The WEBCORE system allows patients to skip individual items when completing the online form. Therefore, we will tabulate the number of missing items from each of the included questionnaires in this study (BPI, QLQ-C30, and CTCAE). These will be reported descriptively, to assess if any particular items are skipped with excess frequency compared to others. Based on prior WEBCORE studies, however, we anticipate that the frequency of skipped individual items will be very low (~1%). In addition, as a part of the overall feasibility evaluation, we will tabulate the frequency with which patients fail to complete the entire form on schedule.

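### The 58/79 pass mark carries a 7.1% type I error, not the stated 4%; the stated 4% and 90% fit 59/79, and three other sections give a different 80% criterion

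*Combined protocol and SAP*

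**What the plan says.** Section 11.1 sets the hypotheses (65% too low, 80% acceptable), requires 79 patients, and describes the test as "with 90% power and type I error of 4" percent. A responder logs in and completes at least half of the questionnaire on at least 4 of 7 occasions. The decision rule is "If at the end of the study 58/79 are responders then the study will conclude" that use of the system is feasible. Section 11.2 repeats the count: "If at the end of the study 58/79 are responders (a responder is a person", and links a pass to larger-scale evaluation.

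Sections 4.1.2 and 11.1 also say that "the accrual period will remain open until at least 80 evaluable patients are enrolled". The planned sample size in 11.1 is 110, while section 4.1 speaks of eighty patients being recruited.

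Three other sections state when larger-scale evaluation is warranted, without the half-completion requirement:

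- Section 1.3: "If 80% of enrolled patients with home Internet access login to WEBCORE at least four times during the study period"
- Section 4.1: "if approximately 80% of enrolled patients login to WEBCORE at least four times"
- Section 9.1: "if approximately 80% of participants login to WEBCORE at least four times during the study period"

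**The concern.** The count in sections 11.1 and 11.2 is the only feasibility rule with stated error rates. If 58 does not deliver 4% and 90%, the primary conclusion rests on a false-positive rate that the plan does not disclose.

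Two further features leave the verdict undetermined. Under the plan's own accrual rule the final denominator should be 80 or more, where no cutoff exists. The 80% statements also attach the same conclusion to a higher threshold and a looser definition, so a result between the two thresholds could be reported either way, depending on the section consulted. Choosing between them after seeing the data would undermine the result.

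**Working it through.** **Inputs** (section 11.1): p0 = 0.65, p1 = 0.80, n = 79, pass mark 58, stated type I error 4%, stated power 90%. Sidedness is not stated; a single-arm rule with an upper cutoff is one-sided.

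**1. Is the stated sample size sound?** The one-sample normal approximation is

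n = [(z(0.96)·√(p0(1−p0)) + z(0.90)·√(p1(1−p1))) / (p1−p0)]²
= [(1.751 × 0.477 + 1.282 × 0.400) / 0.15]² ≈ 80.7.

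That is within two patients of 79. A two-sided 4% gives about 99 and does not fit. By exact binomial search, 79 is the smallest n with type I error below 4.5% and power of at least 90%, and its cutoff is 59.

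**2. Error rates of the pass mark.** Type I error is P(X ≥ r) for X ~ Bin(79, 0.65). Power is the same tail at 0.80.

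| Pass mark | Proportion | Type I error | Power |
|---|---|---|---|
| ≥ 58 (as written) | 73.4% | 7.13% | 94.1% |
| ≥ 59 | 74.7% | 4.33% | 90.4% |
| ≥ 60 | 75.9% | 2.48% | 85.1% |
| ≥ 64 (strict 80%) | 81.0% | 0.14% | 47.8% |

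The stated 4% and 90% are reproduced, to the whole percent, at 59 and not at 58. Normal approximations do not rescue 58: they give 5.8% without continuity correction and 7.3% with it. The ratio to the claim is 7.13/4 ≈ 1.8.

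**3. Denominators other than 79.** At n = 80, keeping the literal count of 58 gives a type I error of 9.7%. If 58/79 is carried forward as a proportion, rounding up (an assumption, since the plan gives no such rule), 59/80 gives 6.1%, 67/90 gives 3.6% and 81/110 gives 3.4%. Over n = 80 to 110 the range is 2.4% to 6.4%. It is above 4% at 16 of 31 values and above 5% at six (80, 81, 83, 84, 87, 91). The excess therefore lies mainly near the accrual minimum.

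**4. The 80% criterion.** 0.80 × 79 = 63.2, so a strict reading needs 64. Results of 58 to 63 pass section 11 and miss 80%. Assume a true rate of 80% and that the login count equals the responder count. The probability that the two rules disagree is then:

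| 80% read as | Against ≥ 58 | Against ≥ 59 |
|---|---|---|
| 64/79 (strict) | 0.9415 − 0.4777 = 46% | 0.9040 − 0.4777 = 43% |
| 62/79 (78.5%, a lenient reading chosen here) | 0.9415 − 0.6913 = 25% | 0.9040 − 0.6913 = 21% |

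Section 11.5 expects about 1% of items to be skipped. That makes near-equality of the two counts plausible but does not establish it.

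**The case against.** The arithmetic is not in dispute; the case against is about weight. The correction at n = 79 is one responder in a pilot whose only consequence is a larger study. It changes the verdict only when exactly 58 respond, which has probability 2.8% at a true 65% and 3.7% at a true 80%. That stands, and it bounds the effect of the miscounted pass mark at n = 79.

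That 58 is the largest failing count written as the passing one is an inference. The 4.5% limit in the search was chosen to match rounding to 4%: a limit of 4.0% gives n = 83 with cutoff 62, and 5% gives n = 75 with cutoff 56. This also stands, but the mismatch between 58 and the stated error rates does not depend on how 58 arose.

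Sections 4.1 and 9.1 say approximately, and 9.1 calls the criterion crude, so section 11 can be read as making a loose target operational. This softens the conflict in two of the three places. It does not remove it: section 1.3 has no such qualifier, 73% to 75% is a generous reading of approximately 80%, and the responder definitions differ.

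Finally, one could keep 58/79 and restate its properties as 7.1% and 94.1%. That would be consistent too, if the sponsor accepts that error rate.

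**Conclusion.** The concern holds. The pass mark and the stated error rates in section 11 do not belong together: 58/79 has an exact type I error of 7.1% against a claimed 4%, and the stated pair fits 59/79. The hypotheses and the sample size are sound.

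The one-responder slip is small. The larger practical risk is that the primary verdict is not uniquely determined, because no cutoff is given for the 80 or more evaluable patients the plan requires and a second criterion leads to the same conclusion. The error rates rest only on the stated inputs and a one-sided exact binomial test. The disagreement probabilities (21% to 46%) also assume a true rate of 80%, coinciding login and responder counts, and a chosen reading of 80%.

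**What to change.** - **Sections 11.1 and 11.2:** replace the count with at least 59/79 (exact type I error 4.3%, power 90.4%).
- **Other evaluable numbers:** add that the cutoff is the smallest r with exact P(X ≥ r | 65%) below 4.5%, stating openly that this limit matches the rounded 4%. Examples: 60/80 (3.7%, power 89.3%), 67/90 (3.6%, 92.3%), 81/110 (3.4%, 95.9%).
- **Sections 1.3, 4.1 and 9.1:** refer to this rule, or state that 80% is the target rate for which the test is powered and not a second pass mark. As a strict pass mark, 80% would have only 47.8% power at a true 80%.
- **Throughout:** use one responder definition, and reconcile the eighty patients in section 4.1 with 110 enrolled and at least 80 evaluable.

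The cost is wording in five sections, with no extra patients. The pass mark at n = 79 rises by one. Power dips below 90% at some numbers in the low-to-mid 80s (lowest 87.0%, at 62/82). A strict limit of 4.0% would need 60/79, with power 85.1%. If the sponsor prefers to keep 58/79, the stated error rates must change to 7.1% and 94.1%, and the other items still apply.

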## Memorial Sloan-Kettering Cancer Center IRB Protocol

**IRB#: 08-155A(8)**

Based on prior MSKCC research in this population, we anticipate that 90% of approached patients will agree to participate, of which 75% will be regular email users [13]. We will track the proportion of patients approached who consent as one of the measures of feasibility. The proportion of patients approached versus consented will be tracked continuously by the Research Fellow and the designated Surgery RSA. There are approximately 570 laparotomies performed on the gynecology service annually (internal data). We anticipate that accrual for the study will be complete within 6-9 months. We will enroll the first 5 patients of 110 patients as a small pilot to identify potential problems and correct any issues that may arise. After the evaluation of the first 5 patients the accrual period will remain open until at least 80 evaluable patients are enrolled. The sequence of patient activities following accrual is shown in Figure 1.

**Figure 1: Sequence of Patient Activities**

**Memorial Sloan-Kettering Cancer Center  
IRB Protocol**

**IRB#: 08-155A(8)**

**11.2 Primary Objective**

The primary objective of this study is to evaluate the feasibility of patients using WEBCORE to track their own symptoms and HRQL while recovering from laparotomy for presumed or confirmed gynecologic cancer. We will calculate summary statistics for several measures of utilization, including the frequency with which each user logs in and completes a WEBCORE online questionnaire; the proportion of patients who log in at each sequential week of follow-up; and when utilization occurs in relation to surgery and/or complications. If at the end of the study 58/79 are responders (a responder is a person who has logged in at least 4/7 times and completed at least half of the questions each time) then we will conclude that the use of WEBCORE in this population is feasible. If this hypothesis is true, we will consider the study results to suggest that WEBCORE is a strategy warranting larger scale evaluation [13]. Baseline patient characteristics and disease information will be examined via a logistic regression for their relationship to a patient's likelihood of being a responder. The following predictors will be considered: type of cancer, type of surgery, stage of disease, computer experience/age/education

In our analysis, we will look at WEBCORE utilization (1) over time and (2) in relation to the presence or absence of documented minor and major surgical complications. We will tabulate the proportion of users who logged in with or without a follow-up reminder email. We will assess for attrition of compliance over time by measuring the proportion of patients who login during each consecutive week of observation. Results of backup telephone calls made when patients have not logged in will be tabulated to assess if the reported symptoms of such patients differ from reports of patients who have logged in on time, and reasons for non-compliance. We will calculate the proportion of WEBCORE responders compared to the total number of enrollees (responders: enrollees), as well as the proportion of responders compared to total number of patients eligible (responders: eligible). Baseline characteristics for those who refuse enrollment will be compared to those who agree to participate.

**11.3 Secondary Outcomes for Patients**

QOL Measures:

EORTC, and Individual Symptom Items (ISI, NCI-CTC) as described in section 7 will be collected at predefined time points. A composite score for the EORTC questionnaire will be calculated following the EORTC scoring manual at each time point. In addition, individual items from these instruments will be summarized at each time point and patients' profiles over time will be described graphically to assess which of these items fluctuate over time, or whether they capture patients' symptoms in this post-op period.

## Memorial Sloan-Kettering Cancer Center IRB Protocol

**IRB#: 08-155A(8)**

### Exit survey:

Patient assessment of the usefulness of WEBCORE will be measured via an exit patient satisfaction questionnaire which will be given via WEBCORE website. This will take place between 6 and 8 weeks post-operatively, and will be given online via WEBCORE website (Appendix 2). Items in this questionnaire are adapted from validated measures used in prior studies evaluating satisfaction with information technology interventions [50-54] and instruments developed by the Picker Institute [55], and makes use of an ordinal scale for recording responses.

Patients who recover quickly from surgery may choose not to use WEBCORE because they feel well, whereas patients experiencing the most severe post-operative symptoms or complications may feel too ill to login. The follow-up telephone call for those who fail to login is intended to address such questions. In addition, in the patient exit survey, questions will specifically address reasons why WEBCORE was not used (Appendix 2). The exit survey will be summarized descriptively in order to understand whether patients failed to use WEBCORE because of technical obstacles, or severity of symptoms, or if they used WEBCORE in a limited fashion despite their symptoms. We anticipate that WEBCORE may be utilized less frequently by patients with the worst symptoms.

